4.0 SUBJECT INCLUSION AND EXCLUSION

Approximately forty eight (48) subjects with diabetes will be enrolled.

Inclusion Criteria

The subject must:

- Be aged 18-75 years, male or female
- Read and understand English
- Have diagnosis of type 1 (goal is 40% to 70%) or insulin-using type 2 diabetes for at least 6 months
- Be taking multiple daily insulin injections (MDI) of at least two pre-meal bolus insulin injections daily or using an insulin pump (Goal is not more than 30% of subjects using insulin pump therapy)
- Performing self-monitoring of blood glucose at home at least twice daily
- Have an iOS mobile device or Android mobile device with Bluetooth capability
 - iOS device: iPod, iPad, or iPhone 5 or later version with iOS 9.x or 10.x software
 - Android: smart phone, software version 5.x or 6.x.
 - Bluetooth: software version 4.0 or higher
- Agree NOT to update the software on their mobile device until after the study is concluded, as follows:
 - No updates of Android device to upcoming Android version 7 (Nougat)
- Be willing to utilize the Contour Next One meter and the Contour Diabetes App 2.0 on personal mobile device which communicates to meter to manage diabetes and be willing to keep a study diary

Exclusion Criteria

- Known Hemophilia or any other bleeding disorder
- Pregnancy (reported by subject; no pregnancy test required)
- Current user of Contour Next One BGMS including Contour Diabetes App.
- Physical, visual or neurological impairments that would make the person unable to perform testing with the Contour Next One BGMS or to use the Contour Diabetes App
- Working for a competitive medical device company, or having an immediate family member or someone who is not a family member but is living within the household of someone who works for such a company.
 - Immediate family members are the subject's parents, spouse, children, and siblings, including the parent's spouse; step children and adopted children and their spouses.

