5.0 MATERIALS AND METHODS

5.1 Study Details

5.1.1 General

- a) This study will evaluate the Contour Diabetes App 2.0 system at one site where study staff have been trained on the Contour Diabetes App and Contour Next One system.
- b) At least forty (40) subjects must complete the study
- c) All subjects will complete the informed consent (IC) process.
- d) Inclusion/exclusion information will be collected. Subjects must meet these criteria to be enrolled in the study.
- e) A unique study number will be assigned to each subject.
- f) The study staff will document subject demographics (including both screen failed and enrolled subjects), diabetes history and management. Subject's responses to demographic and medical history questions will be self-reported. Medical record verification is not required.
- g) Original study data reported at the clinic will be collected on paper structured source documents (SSDs). Study staff will complete all SSDs. Laboratory reports for A1C and fructosamine will serve as their own source docs. Electronic data collection (EDC) will be used for permanent data storage and will be entered by site staff.
- h) The subject will be informed that, if during the course of participating in this trial, he/she would need to perform a personal diabetes management procedure, verification of blood glucose measurements should be performed with the user's typical pre-study procedures.

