11.0 STATISTICAL METHODS AND ANALYSIS

An $n = 40$ responses yields approximately a 93.3% chance of “passing” the primary objective criteria if there is an 85% probability that a randomly selected person could perform the critical tasks successfully.

Performance Criteria for subject’s success at utilizing system features:

There is at least an 85% probability that any user would be able to utilize the App features with success. A hypothesis test will be performed to test the hypotheses for each feature individually:

$$H_0 : \Pr\{user\ can\ perform\ a\ given\ basic\ task\ successfully\} < 85\%$$

against:

$$H_1 : \Pr\{user\ can\ perform\ a\ given\ basic\ task\ successfully\} \geq 85\%$$

With $n = 40$ responses, we must observe at least 31 responses with a 1, 2, or 3 score on a critical questionnaire statement (statements 1, 8, 9, and 42 as shown in Appendix A) to reject the null hypothesis, H_0 . This criterion yields the following risk characteristics:

There is approximately a 93.3% chance (power) of obtaining at least 31 “successes” out of $n = 40$ responses IF the actual probability of success is 85%. Conversely, there is approximately a 90% chance of failing to obtain at least 31 successes out of $n = 40$ responses IF the actual probability of success is only about 66.8%.

It is likely that the actual sample size will not be exactly 40, but in fact may be slightly higher or lower. Responses of “no opinion” will not be counted for any hypothesis test. The critical values for hypothesis tests will be adjusted for sample size, to maintain approximately the same power characteristics, i.e., the probability of rejecting the null if the success probability is 85% will be kept to be no greater than 95%.

The results accessing each feature will be evaluated independently. Statements 1, 8, 9, and 42 in Appendix A correspond to the primary endpoint and the 85% criterion.

Cluster Analyses and Other Associated Analyses

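### The rule for adjusting the cut-off when n is not 40 is only a ceiling on the chance of passing at a true 85%, so it cannot hold the stated power or support a claim of at least 85% success

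*Combined protocol and SAP*

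**What the plan says.** Section 11.0 tests each of statements 1, 8, 9 and 42 separately. The null hypothesis is that the success probability is below 85%; the alternative is that it is 85% or more. At n = 40, "we must observe at least 31 responses with a 1, 2, or 3 score on a critical questionnaire statement" for the null to be rejected. Two operating characteristics follow. "There is approximately a 93.3% chance (power) of obtaining at least 31" successes when the true probability is 85%, and "there is approximately a 90% chance of failing to obtain at least 31 successes" "IF the actual probability of success is only about 66.8" per cent.

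The plan then says "It is likely that the actual sample size will not be exactly 40" and that critical values will be adjusted so that power stays roughly where it was. It spells this out in one numerical condition: "the probability of rejecting the null if the success probability is 85% will be kept to be no greater than 95" per cent. It gives no lower limit, no condition at 66.8%, no significance level for these tests and no table of cut-offs.

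Three other provisions bear on n. Section 5.1.1 states "At least forty (40) subjects must complete the study", and Section 4.0 states "Approximately forty eight (48) subjects with diabetes will be enrolled". Section 11.0 leaves no-opinion answers out of the tests and treats hardware or software failures as un-evaluable, so n can differ between the four statements and can fall below 40 even with 40 completers.

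**The concern.** The adjustment rule sets the pass mark for all four primary statements in the situation the plan itself calls likely. To maintain power, a rule needs a lower limit on the chance of passing at 85%. This one has only an upper limit.

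The limit also sits at the edge of the null hypothesis. The rejection probability at a true 85% is the largest type I error the test can have, and the plan labels it power. Capping it at 95% gives almost no protection against rejecting a true null, so a pass cannot carry the meaning that the written hypotheses give it.

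At stake are whether two statisticians would apply the same pass mark at a given n, whether the published 93.3% and 90% describe the test actually run, and what a pass may be said to show.

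**Working it through.** **Inputs.** From Section 11.0: n = 40, cut-off k = 31, true probabilities 85% and 66.8%, ceiling 95%. The plan gives no range for n beyond a little above or below 40. I assume n = 38 to 48 as the main range, the top being planned enrolment, and use n = 34 to 37 to show what happens with more exclusions.

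**Formula.** X is binomial(n, p) and the chance of passing is P(X ≥ k | n, p), computed exactly.

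**Step 1: the plan's figures.**
- P(X ≥ 31 | 40, 0.85) = 0.9328; stated 93.3%.
- P(X < 31 | 40, 0.668) = 0.9004; stated 90%.

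Both reproduce.

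**Step 2: what the ceiling fixes.** P(X ≥ k) falls as k rises, so the ceiling sets a minimum k and no maximum. At n = 40, k = 30 gives 97.0% and is excluded. Every k from 31 to 40 complies: 93.3% at 31, 86.5% at 32, 60.7% at 34, down to 0.15% at 40.

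**Step 3: aim against ceiling.** For each n, compare the k whose P(X ≥ k | n, 0.85) is closest to 93.3% with the smallest k under the ceiling.

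| n | k closest to 93.3% | Pass at 85% | Smallest k under ceiling | Pass at 85% |
|---|---|---|---|---|
| 38 | 29 | 95.05% | 30 | 89.4% |
| 43 | 33 | 95.12% | 34 | 89.9% |
| 48 | 37 | 95.22% | 38 | 90.4% |

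At these n the two instructions give different pass marks. At n = 38, exactly 29 successes would pass under one and fail under the other; the chance of passing at 66.8% is 14.1% with k = 29 and 7.5% with k = 30. At n = 37 the two candidates (95.8% and 90.8%) are almost equally far from the target and the answer turns on rounding, so I do not count it.

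**Step 4: the natural reading, smallest k under the ceiling.**

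| n | k | Pass at 85% | Fail at 66.8% |
|---|---|---|---|
| 34 | 26 | 94.1% | 84.5% |
| 36 | 28 | 92.0% | 89.1% |
| 38 | 30 | 89.4% | 92.6% |
| 39 | 30 | 94.2% | 88.1% |
| 40 | 31 | 93.3% | 90.0% |
| 42 | 33 | 91.1% | 93.1% |
| 44 | 34 | 94.3% | 90.9% |
| 48 | 38 | 90.4% | 95.6% |

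Over n = 38 to 48 the chance of passing at 85% runs from 89.4% to 94.3%. The chance of failing at 66.8% is at least 90.0% at every n from 40 to 48, but not at 34, 36 or 39.

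**Step 5: the edge of the null.** At n = 40 and k = 31, a true probability of 84.9%, where the null is true, passes with probability 93.0%. The pass mark is itself an observed rate of 31/40 = 77.5%.

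**The case against.** The best defence is that the ceiling explains a broader instruction to keep power roughly unchanged, and that read together they point to the smallest k under the ceiling. That k is unique for each n, returns 31 at n = 40 and drifts little nearby. Most of this stands. A reader might infer that the rule would allow a demand for 40 out of 40; the broader instruction excludes that. What does not stand is that the text says so: the word smallest is absent, and at n = 38, 43 and 48 the instruction and the ceiling point to different cut-offs. The breaches are small, 0.05 to 0.22 points, but one response can decide a primary endpoint.

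A reader might also infer that false passes are unlimited. They are not: the minimum k also bounds the chance of passing at 66.8%, to at most 9.96% for every n from 40 to 48. Nor does the ceiling leave room to ease the pass mark once the counts are known, since it already fixes the most lenient cut-off at each n; any other compliant choice makes passing harder.

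Finally, n near 30 would produce larger departures, but that would need about ten exclusions on one statement among 40 completers, and nothing in the documents suggests this.

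**Conclusion.** The concern holds in a limited form and should be fixed. The adjustment rule is a ceiling where maintaining power needs a floor. It conflicts with its own aim at n = 38, 43 and 48, and it permits up to 95% rejection at the edge of the written null. The last point has the most consequence: under this rule a pass does not show that at least 85% of users succeed.

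The numerical drift is modest on the natural reading. For n = 38 to 48, power at 85% stays within about four points of the stated 93.3%. The stated 90% is kept from 40 upward and missed at some smaller n, by about two points at 39 and five to six at 34. These sizes rest on exact binomial tails, independent responses within a statement and the assumed range of n. The documents do not support a stronger conclusion that the rule leaves the pass mark wholly open or false passes unbounded.

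**What to change.** Replace the ceiling in Section 11.0 with an exact rule and a printed table of cut-offs by n, fixed before any responses are seen and applied to each statement at its own n.

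If the sponsor keeps the 31-of-40 acceptance rule, state what it tests: null hypothesis p ≤ 66.8% at one-sided 10%, with k the smallest integer for which P(X ≥ k | n, 0.668) ≤ 0.10.

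| n | k | Pass at 85% | Pass at 66.8% |
|---|---|---|---|
| 38 | 30 | 89.43% | 7.45% |
| 39 | 31 | 87.99% | 6.12% |
| 40 | 31 | 93.28% | 9.96% |
| 41 | 32 | 92.26% | 8.31% |
| 42 | 33 | 91.14% | 6.91% |
| 43 | 34 | 89.94% | 5.71% |
| 44 | 34 | 94.34% | 9.15% |
| 45 | 35 | 93.49% | 7.67% |
| 46 | 36 | 92.55% | 6.40% |
| 47 | 36 | 95.87% | 9.95% |
| 48 | 37 | 95.22% | 8.41% |

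Extend the table below 38 in case exclusions are heavier; at n = 36 the rule needs 29, with 83.8% power at 85%. Report the chance of passing at 85% beside each cut-off, and do not describe a pass as rejecting p < 85%.

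The cost is one sentence and a table, with no extra data. There are two drawbacks: power at 85% varies with n (88.0% to 95.9% here, lower at some smaller n), and the claim that a pass supports is weaker. Against the smallest-k reading, the pass mark rises by one at n = 39 and falls by one at 47 and 48.

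Testing the written null at one-sided 5% is a separate choice that I would not require. It needs 38 of 40 (P = 4.86% at 85%) and would pass only about 22% of the time at a true 90%.

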Contour Diabetes App 1.0 includes notifications of “Critical High” and “Critical Low” blood glucose patterns if recognized in the patient data. Smart test plans (also called Smart Reminders) can help the user manage personal diabetes care regimens by providing pre-set test and appointment reminders. Basic testing plans are included in App 1.0. The App includes a Cloud Services Platform which offers online remote storage of user data and account information. User data is synchronized with the Cloud and with other customer owned devices.

Contour Diabetes App 1.0 was tested in the hands of people with diabetes in a study conducted at one clinical site in the US¹. This study enrolled 45 persons with diabetes (type 1 or type 2 diabetes on insulin therapy) who used the Contour Next One meter and Contour Diabetes App as part of their routine diabetes management at home for 3 weeks. At the end of the study, subjects completed a questionnaire about their experiences using the system. In summary 95% of subjects reported they were able to successfully sync their blood results on the meter with the App, as well as access and interpret the blood glucose displays in the App.

¹ Bailey T, Davis T, Wallace J, Pardo S, Morin R, *Usability of a New Blood Glucose Monitoring System (BGMS) With A Mobile App*, poster presented at the 76th Annual American Association of Diabetes Meeting, June 12, 2016, New Orleans, LA

In addition, the accuracy of the Contour Next One system was demonstrated in laboratory and clinical settings. In a clinical user evaluation study, with 329 patients with diabetes, 99.4% of the Contour Next One results were within $\pm 15\text{mg/dL}/15\%$ of the laboratory reference results.² These results met the International Standard ISO 15197:2013(E).

The Contour Next One BGMS with Contour Diabetes App 1.0 has received CE mark and has been commercially launched in Europe. Note that this study will test the next release version of the Contour Diabetes App 2.0.

Contour Diabetes App 2.0

The Contour Diabetes App 2.0 is an updated version of the CE marked Contour Diabetes App 1.0.

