2.0 OBJECTIVES

Primary Objective:

The purpose of this study is to assess the utility of the Contour Diabetes App 2.0 when used with the Contour Next One meter (the Onyx system) in the hands of subjects with type 1 diabetes or insulin-using subjects with type 2 diabetes. It is designed to determine the subjects’ self-reported success in utilizing the features of the system. Each feature will be evaluated independently, by including a series of statements about each feature set for which a numerical score or rating will be provided by subjects. The evaluation includes:

- Obtain a synced blood glucose reading

² Christiansen M, Greene C, Pardo S, Warchal-Windham ME, Harrison B, Morin R, Bailey T, *Accuracy and User Performance Evaluation of a New Blood Glucose Monitoring System in Development For Use With CONTOUR Next Test Strips*, Poster presented at the 15th Annual Diabetes Technology Meeting (DTS), Oct 22, 2015, Bethesda, MD

- Recognize and use “Smart Reminders”
- Access and interpret glucose displays such as Expanded Graph and My Readings views
- Recognize glucose pattern notifications (as applicable since all subjects may not receive pattern messages)

Goal: For the following features, at least eighty five percent (85%) of potential users should be able to report that they were able to successfully utilize the feature. A rating of 1, 2, or 3 for each feature (1=strongly agree, 2=agree, 3=neither agree nor disagree, 4=disagree, 5=strongly disagree) indicates that the subject was able to successfully utilize the feature. These include:

- Obtain a synced blood glucose reading
- Recognize and use “Smart Reminders”
- Access and interpret glucose displays such as Expanded Graph and My Readings views.

Other Objectives:

1. Ease of Use: Determine ease of use of the Contour Diabetes App 2.0 when used with the Contour Next One meter via subjects’ self-assessment.
2. Hypoglycemia Frequency: Report severe hypoglycemia events
3. Glycemic Control: Measure changes in hemoglobin A1C and fructosamine levels
4. Total daily insulin dose: Evaluate changes in self-reported insulin doses throughout the study. Both bolus and basal insulin doses are reported and, if insulin varies from day to day, average units will be reported.
5. Clarity of User Instructions: Obtain the subjects’ ratings on the clarity and utility of the instructions.

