6. Subject Feedback: Obtain the subjects’ opinions about their experiences using the Contour Diabetes App 2.0 in conjunction with the Contour Next One meter system.
7. Overall experience with the system Hardware/Software: Obtain data on hardware/software failures and unexpected events using the App.
8. Weight/BMI: Measure changes in weight and BMI
9. Feature Utilization rates (from cloud data)

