Ordinal-scaled variables from ease of use and diabetes management attitude surveys will be used in a k-means cluster analysis, to assess the possibility of unknown groupings (clusters) of subjects within the study sample. Other variables, such as diabetes type, age, gender, and frequency of blood glucose testing will be used to potentially further characterize the groupings. Inasmuch as there is no a priori expectation for the numbers of clusters, nor is there any expectation or hypotheses that any variables will have associations with clusters, these analyses should be considered exploratory.

A condition of hardware/software failure that cause or contribute to a subject's inability to access or utilize any given feature will be considered an un-evaluable observation. (i.e., will not be included in the numerator/denominator for calculating percentage of user success.)

Frequency distributions of scores will be provided for the other variables, i.e., subjects' ratings on ease of use and subjects' ratings on clarity/utility of user instructions, subjects' opinions about their use of the Contour Diabetes App 2.0 system. Correlation coefficient, and associated 95% two-sided confidence interval, will be computed for laboratory HbA1c versus average glucose. Average glucose will be computed from cloud data.

Histograms for the change in HbA1c, fructosamine, weight, and total daily insulin (as reported by subjects) from visit 1 to visit 2 will be constructed. ANOVA (or equivalent method) will be used to determine whether change in HbA1c, Fructosamine, weight, and total daily insulin are significantly different from zero. P-values less than or equal to 0.05 will be considered significant. Confidence intervals (95%, two-sided) for the average change in HbA1c, fructosamine, weight, and total daily insulin dose will be computed.

Average daily utilization rates for selected App features will be computed, together with 95% (non-simultaneous) confidence intervals. Frequency tables for discrete demographic variables will be constructed. Descriptive statistics, such as mean, standard deviation, median, minimum, maximum will be computed for continuously-valued demographic variables (e.g., subject age).

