Appendix A – Contour Diabetes App 2.0 Questionnaire

Obtain a synced blood glucose reading

1. Overall, I was able to successfully sync my blood glucose value on the meter with the App.

1= Strongly Agree

2= Agree

3= Neither Agree nor Disagree

4= Disagree

5= Strongly Disagree

No opinion

2. Overall, I am satisfied with how easily my blood glucose value on the meter syncs with the App.

1= Strongly Agree

2= Agree

3= Neither Agree nor Disagree

4= Disagree

5= Strongly Disagree

No opinion

3. The syncing of my blood glucose value from the meter to the App is reliable.

1= Strongly Agree

2= Agree

3= Neither Agree nor Disagree

4= Disagree

5= Strongly Disagree

No opinion

4. The syncing of my blood glucose value from the meter to the App is accurate.

1= Strongly Agree

2= Agree

3= Neither Agree nor Disagree

4= Disagree

5= Strongly Disagree

No opinion

5. Did you change time zones during the study? Yes or No

6. If Yes, did the App adjust to the time zone change as expected or did you experience any problems? Please comment below.

(open text field)

7. Do you have any comments about syncing of the meter with the App?

(open text field)

Access and interpret glucose displays such as expanded graph and sequential views.

8. Overall, I was able to successfully access glucose displays such as Expanded Graph view and My Readings view in the App.

- 1= Strongly Agree
- 2= Agree
- 3= Neither Agree nor Disagree
- 4= Disagree
- 5= Strongly Disagree
- No opinion

9. Overall, I was able to successfully interpret glucose displays such as Expanded Graph view and My Readings view in the App.

- 1= Strongly Agree
- 2= Agree
- 3= Neither Agree nor Disagree
- 4= Disagree
- 5= Strongly Disagree
- No opinion

10. Accessing the Expanded Graph view was:

- 1= Very Simple
- 2= Simple
- 3= Neither Simple nor Difficult
- 4= Difficult
- 5= Very Difficult
- No opinion

11. Using the Expanded Graph view was:

- 1= Very Simple
- 2= Simple
- 3= Neither Simple nor Difficult
- 4= Difficult
- 5= Very Difficult
- No opinion

12. Expanded Graph View in the App was understandable and easy to interpret.

- 1= Strongly Agree
- 2= Agree
- 3= Neither Agree nor Disagree
- 4= Disagree
- 5= Strongly Disagree
- No opinion

13. Expanded Graph View in the App was helpful for me in managing my diabetes.

1= Strongly Agree

2= Agree

3= Neither Agree nor Disagree

4= Disagree

5= Strongly Disagree

No opinion

14. Accessing the My Readings view was:

1= Very Simple

2= Simple

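### Failure-related inability to use a feature is removed from the primary success percentage, although the 85% goal is stated for potential users of the App with the meter

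*Combined protocol and SAP*

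**What the plan says.** The rule is in Section 11.0, under the subheading on cluster and other associated analyses. A hardware or software failure that causes or contributes to a subject's "inability to access or utilize any given feature will be considered an un-evaluable observation". The section adds that such an observation "will not be included in the numerator/denominator for calculating percentage of user success". The only success percentage the plan tests is the primary criterion on statements 1, 8, 9 and 42, so the rule must apply there.

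The goal is wider. Section 2.0, repeated in Section 3.0, asks that at least 85% "of potential users should be able to report that they were able to successfully utilize the feature". The object assessed is the App used together with the meter. Section 11.0 gives the performance criterion as: "There is at least an 85% probability that any user would be able to utilize the App features with success".

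Three other provisions bear on the point:
- No-opinion answers "will not be counted for any hypothesis test" (Section 11.0).
- Statement 1 in Appendix A reads: "Overall, I was able to successfully sync my blood glucose value on the meter with the App".
- Item 7 of the other objectives in Section 2.0 is: "Obtain data on hardware/software failures and unexpected events using the App".

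**The concern.** Whether an observation is excluded depends on the outcome: it is dropped because the subject could not use the feature. The remaining percentage answers whether users succeed when the system works. The goal asks whether potential users succeed with the system.

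The conflict is sharpest for statement 1. Syncing is itself a function of hardware and software, so a sync failure caused by the product is a direct route to non-success, yet it is deleted. The conflict is weakest for statement 9, which asks about interpreting displays.

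At stake are the reported percentage and, if failures are common or success is near 85%, the pass decision. The plan does not say who decides that a failure contributed, or whether that person has seen the rating. It plans no all-users analysis.

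**Working it through.** **Inputs from Section 11.0.** n = 40; pass with at least 31 ratings of 1, 2 or 3. For other n the critical value is re-set so that the chance of passing at 85% does not exceed 95%. I read this as the smallest r with P(X ≥ r | n, 0.85) ≤ 0.95, and take the pass rule as given.

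**The plan's own figures.** P(X ≥ 31 | 40, 0.85) = 0.9328 (stated 93.3%). 1 − P(X ≥ 31 | 40, 0.668) = 0.9004 (stated about 90%). Both reproduce. The reading above gives r = 31 at n = 40 and r = 27 at n = 35 (P = 0.931).

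**Assumptions.** The documents give no failure rate. Let f be the share of subjects affected, taken as 2, 5, 10 and 20%, and u the success rate among unaffected subjects. I use u = 85% (the goal) and u = 95%. The latter is borrowed from the App 1.0 study in Section 1.0, where "95% of subjects reported they were able to successfully sync their blood results on the meter with the App", and is indicative only.

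**Upper bound: no affected user succeeds.** All-users success is u(1 − f), and the percentage reported under the exclusion is u. The pass chance with failures counted is P(X ≥ 31 | 40, u(1 − f)). With exclusion, the number dropped is Binomial(40, f) and the critical value is re-set for each remaining n.

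| u | f | All users | Reported | Pass, failures counted | Pass, excluded |
|---|---|---|---|---|---|
| 85% | 2% | 83.3% | 85% | 88.1% | 93.0% |
| 85% | 5% | 80.8% | 85% | 77.1% | 91.9% |
| 85% | 10% | 76.5% | 85% | 52.8% | 91.7% |
| 85% | 20% | 68.0% | 85% | 13.0% | 91.6% |
| 95% | 2% | 93.1% | 95% | 99.97% | >99.9% |
| 95% | 5% | 90.3% | 95% | 99.6% | >99.9% |
| 95% | 10% | 85.5% | 95% | 94.4% | >99.9% |
| 95% | 20% | 76.0% | 95% | 49.8% | >99.9% |

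**Milder case: half of affected users rate 1–3 and stay in; the other half are excluded.** All-users success is S = u(1 − f) + 0.5f, and the reported percentage is S/(1 − 0.5f). For u = 85% and f = 10%: S = 0.765 + 0.05 = 0.815, reported 0.815/0.95 = 0.858.

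| u | f | All users | Reported | Pass, all ratings kept | Pass, excluded |
|---|---|---|---|---|---|
| 85% | 2% | 84.3% | 85.2% | 91.4% | 93.7% |
| 85% | 5% | 83.3% | 85.4% | 88.0% | 93.7% |
| 85% | 10% | 81.5% | 85.8% | 80.7% | 93.9% |
| 85% | 20% | 78.0% | 86.7% | 61.8% | 95.5% |
| 95% | 2% | 94.1% | 95.1% | 99.99% | >99.9% |
| 95% | 5% | 92.8% | 95.1% | 99.96% | >99.9% |
| 95% | 10% | 90.5% | 95.3% | 99.65% | >99.9% |
| 95% | 20% | 86.0% | 95.6% | 95.5% | >99.9% |

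**When all-users success falls below 85%.** In the upper bound, when f > 1 − 0.85/u, which is 10.5% at u = 95% and 5.6% at u = 90%. In the milder case at u = 95%, when 0.95 − 0.45f < 0.85, that is f > 0.10/0.45 = 22.2%.

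**One example.** With 5 of 40 excluded, 27 of 35 (77.1%) passes. If none of the 5 succeeded, that is 27 of 40, or 67.5%.

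**The case against.** The strongest reply is that the rule was fixed in advance and fits part of the text. The hypotheses in Section 11.0 concern whether a user can perform a basic task, and the excluded quantity is a percentage of user success. If the target is user performance, setting product faults aside is defensible, and the term potential users names a population without saying how malfunctions are scored. This stands as a possible target. It does not remove the conflict, because the stated goal nowhere limits itself to a working system.

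A reader might infer that failures are hidden. The documents do not support that. Failures are an objective in their own right, feedback on them is collected at about days 14, 28 and 42 (Appendix C), and statements 2 to 4 ask about ease, reliability and accuracy of syncing. None of this corrects the primary percentage.

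The upper bound is also harsh. Statement 1 asks about success overall, a neutral rating counts as success, syncing is checked at Visit 1 and technical support is available. A passing fault need not make a subject unable to use the feature, and the clause reaches only failures tied to inability. The milder case is therefore shown alongside.

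Finally, the App 1.0 figure is a share of subjects, with no statement that failures were excluded, so using it for unaffected users is an assumption. If it covers all users, a failure rate of 10 to 20% with no affected user succeeding would not fit it, though that concerns App 1.0 only.

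**Conclusion.** The goal and the primary analysis disagree, and the text should be changed. Followed as written, the rule gives a percentage that is too high whenever qualifying failures occur and affected subjects succeed less often than the rest.

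The size rests on an assumed failure rate. With 85% success among unaffected users and f = 10%, the overstatement is 4.3 percentage points in the milder case (85.8 − 81.5) and 8.5 in the upper bound (85 − 76.5). The pass chance under exclusion stays near 92% in the upper bound at f of 5 to 20%, while it falls from 77.1% to 13.0% if failures count. With 95% among unaffected users, the pass decision changes materially only if failures are common and few affected users succeed.

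Two stronger readings are tempting:
- That the reported percentage is overstated in any event. It is not: with no qualifying failure nothing changes, and the documents give no rate.
- That the exclusion is why 27 of 35 passes at 77.1%. It is not: the plan already passes 31 of 40 (77.5%). Only the further step to 67.5% comes from the exclusion, and only if all five excluded subjects were non-successes.

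**What to change.** In the primary analysis text of Section 11.0:
- Keep every subject's own 1–5 rating on statements 1, 8, 9 and 42 in numerator and denominator, whether or not a failure occurred.
- Report the present exclusion rule as a sensitivity analysis, with the number excluded per statement.
- Leave the no-opinion rule as it is, but report how many such answers were attributed to a failure, and show the percentage with those counted as non-successes.

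If the sponsor prefers user performance given a working system as the primary target, say so in the goal in Sections 2.0, 3.0 and 11.0, decide exclusions without sight of the rating, and report the all-users percentage next to the primary one.

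The cost is wording and one extra table, and the headline percentage may be slightly less favourable. Keeping all ratings needs no new failure classification for the primary analysis. The sensitivity analysis uses the judgement that the present rule already requires, and attributing no-opinion answers to a failure needs a short note when the questionnaire is completed at Visit 2.
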